4.4. Prohibited Medications and Procedures During Study

The definitions of prohibited medications and procedures are described in the Section 7.7.2 of the protocol. They will be reviewed and identified by the study clinician and reported in protocol deviations.

4.5. Patient Disposition

Patient disposition will include the description of patient status at major milestone decisions in the study, as well as the patient analysis populations.

For patient study status, patient milestone categories are defined below. As applicable, percentages will be calculated using a denominator of the number of patients treated with open-label study treatment, with two exceptions. Specifically, the two exceptions will be for the screened and screen failure categories, which will not have associated percentages shown.

- The total number of screened patients: defined as originally having met the inclusion criteria and signed the ICF
- The total number of patients failed screening
- The total number of patients enrolled, defined as all screened patients with a treatment kit number allocated and recorded in the IVRS database, regardless of whether the treatment kit was used.

- The total number of patients enrolled but not receiving study treatment.
- The total number of patients enrolled and receiving study treatment.
- The total numbers of patients who have participated in a previous evinacumab study (i.e., R1500-CL-1331 and R1500-CL-1629), or evinacumab-naïve patients with HoFH.
- The total number of patients who completed the OLTP as collected on the End of Treatment - Evinacumab e-CRF.
- The total number of patients who prematurely discontinued study treatment during the OLTP, and the reasons for discontinuation collected on the End of Treatment - Evinacumab e-CRF.
- The total number of patients ongoing in OLTP (applicable for the interim analyses)
- The total number of patients who complete the last study follow-up visit (i.e. Follow-up week 24).

The following patient populations for analyses are listed below:

- Safety (SAF) Analysis Set
- Efficacy Analysis Set (same as SAF)
- Pharmacokinetic (PK) Analysis Set
- Immunogenicity (ADA and NAb) Analysis Sets

The following patient listings will provide the details from the patient disposition table.

- A listing of patients treated but not enrolled, patients enrolled but not treated.
- A listing of patients prematurely discontinued from treatment, along with reasons for discontinuation.

4.6. Study Treatment Exposure and Compliance Variables

Study treatment exposure variables for infusions administered during the study are listed below with associated definitions:

- Patient duration of open-label study treatment exposure in weeks defined as: (last open-label evinacumab treatment administration date in the study +28 – first open-label evinacumab treatment administration date in the study +1)/7. Unplanned intermittent discontinuations in study treatment will be addressed on a case-by-case basis, since this is expected to be a rare occurrence.
- Patient duration of open-label study treatment exposure in patient-years is calculated as the patient duration in weeks multiplied by 7/365.
- The following categories will be used for treatment exposure intervals: ≥ 1 day and < 4 weeks, ≥ 4 weeks and < 8 weeks, ≥ 8 weeks and < 12 weeks, ≥ 12 weeks and < 16 weeks, ≥ 16 weeks and < 20 weeks, ≥ 20 weeks and < 24 weeks, ≥ 24 weeks and < 28 weeks,

≥28 weeks and <32 weeks, ≥32 weeks and <36 weeks, ≥36 weeks and <40 weeks,
≥40 weeks and <44 weeks, ≥44 weeks and <48 weeks, etc.

- The total number of open-label evinacumab treatment infusions by patient.

With respect to patient treatment administration compliance, the study treatment is administered during the investigative site visits and therefore study compliance will be assessed by infusion frequency for treatment period, specifically:

- for each patient as the average number of days between 2 infusions: (last dose date – first dose date) / (number of infusions in OLTP -1), for patients receiving at least 2 infusions.

All important and minor protocol deviations potentially impacting safety and efficacy analyses, and drug-dispensing irregularities, as well as other deviations, will be collected and reviewed on an ongoing basis throughout the study as described in the Protocol Deviation Plan (PDP). Both monitoring-collected and programmatically derived deviations are listed and defined in the PDP.

4.7. Primary and Secondary Endpoints

4.7.1. Primary Endpoint

The primary endpoint is the incidence and severity of treatment-emergent adverse events (TEAEs) and other safety variables during the open-label treatment period in patients treated with evinacumab 15 mg/kg IV Q4W.

4.7.2. Secondary Efficacy Endpoints

The secondary efficacy endpoints are:

- The percent change in LDL-C from baseline over time
- The absolute change in LDL-C from baseline over time
- The percent change in Apo B from baseline over time
- The absolute change in Apo B from baseline over time
- The percent change in non-HDL-C from baseline over time
- The absolute change in non-HDL-C from baseline over time
- The percent change in TC from baseline over time
- The absolute change in TC from baseline over time
- The percent change in TGs from baseline over time
- The absolute change in TGs from baseline over time

The definition of the baseline value for computation of the change from baseline can be found in Section 6.1.

The secondary efficacy lipid endpoint of the percent change in the lipid endpoint from baseline over time is defined as: $100 \times (\text{lipid value} - \text{lipid value at baseline}) / \text{lipid value at baseline}$.

The baseline lipid value will be the last value obtained according to the definition of baseline specified in Section 6.1. The lipid value at each post-baseline time point will be the lipid value obtained within the global analysis window, regardless of adherence to treatment and subsequent therapies.

All lipid values (scheduled or unscheduled, fasting or not fasting) may be used to provide a value for the secondary efficacy endpoint, if appropriate, with the following exceptions:

- Only fasting TG measurements will be included in the analysis. TG measurements with missing fasting status will be excluded from the analyses.
- On the day of apheresis, any lipid values collected after apheresis for the respective visit will be excluded from the efficacy analyses.

All measurements will be assigned to efficacy analysis windows defined in Appendix 10.2 of this SAP. For all time points post-baseline, the value used for the analyses at a given time point (e.g. at week 24) is the value obtained within the corresponding efficacy analysis window. The baseline value is defined according to the definition of baseline specified in Section 6.1.

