- change to a commercially available PCSK9 inhibitor antibody prior to enrolling into this study

Clinical laboratory samples must be collected and study assessments must be performed before study drug is administered.

Patients who are undergoing apheresis or plasma exchange must have their clinical laboratory samples drawn and study assessments performed before undergoing the procedure. Every effort should be made for the patient to receive study drug immediately after completion of the apheresis procedure, but patients can receive study drug 1 day before the apheresis procedure. Patients undergoing plasma exchange should receive the study drug immediately after completing the procedure. Given the impact of lipoprotein apheresis, PCSK9 inhibitors, and mipomersen on lipid parameters, it is important to match the time of the baseline activities with the timing of the week 24 activities. This would mean that the timing between the baseline sample collection relative to the most recently completed LDL apheresis procedure, administration of a PCSK9 inhibitor or mipomersen should match the timing of the week 24 sample collection relative to the most recently completed apheresis procedure, administration of a PCSK9 inhibitor or mipomersen.

Patients receiving background LMT that has been proven to reduce the risk of ASCVD (eg, statins, ezetimibe, PCSK9 inhibitor antibodies) should make their best effort to maintain a stable regimen after week 24 and for the duration of the study.

Patients receiving other LMT (eg, apheresis, lomitapide) may have that LMT adjusted after week 24, based on their LDL-C levels, CV risk factors, and judgment of the investigator.

Patients should be on a stable heart healthy diet and exercise regimen throughout the duration of the study, starting at the baseline visit and continuing through the end of the open-label treatment period.

Treatment will continue until 1 of the following occurs:

- Clinical development of evinacumab for the indication described in this study protocol is discontinued
- Clinical development of evinacumab is terminated
- Risk/benefit of evinacumab in this patient population is deemed unfavorable
- Evinacumab is approved by the regulatory authority governing the location of the study site*

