4.9. Other Variables

Other assessment endpoints are listed and defined below. Protocol schedule visits will be assigned to the Global Analysis Windows (See Appendix 10.2).

- The change in hemoglobin A1c (HbA1c [%]) from baseline to post-baseline visits.
- The percent change in hs-CRP from baseline over time.
- The percent change in HDL-C from baseline over time
- The percent change in Apo A1 from baseline over time
- The percent change in Apo B/Apo A1 ratio from baseline over time
- The percent change in Lp(a) from baseline over time
- The percent change in Apo CIII from baseline over time

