5.9. Analysis of Other Variables

Summaries for the treatment period will be presented by patient group for the study in the safety analysis set. No formal inferential testing will be performed. Summaries will be descriptive in nature.

All measurements, scheduled or unscheduled, fasting or not fasting, will be assigned to Global Analysis Windows (Appendix 10.2) in order to provide an assessment for all post-baseline visit.

Hs-CRP, HbA1c, HDL-C, Apo A1, and Apo B/Apo A1 ratio, Lp(a), Apo CIII parameters will be summarized for the number of patients with data, mean, SD, median, minimum, maximum, Q1 and Q3 by analysis visit during the treatment period. The medians (with Q1-Q3) will be plotted for hs-CRP, and means (+/- SE) for HbA1c, HDL-C, Apo A1, and Apo B/Apo A1 ratio, Lp(a), Apo CIII. Applying the PCSV criteria at any time during the TEAE period, the number of patients (and percentages) meeting the criteria will be summarized.

The summary of other variables will be provided for all patients in the study in the safety analysis set, and again for the subpopulation of adolescent patients.

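### The post-apheresis exclusion covers only the day of apheresis and is not carried over to the SAP 4.9 variables measured in the same sample

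*SAP*

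**What the plan says.** SAP 4.7.2 opens broadly: lipid values of any kind "may be used to provide a value for the secondary efficacy endpoint, if appropriate, with the following exceptions". One exception concerns fasting status for triglycerides. The other is the apheresis rule: "On the day of apheresis, any lipid values collected after apheresis for the respective visit will be excluded from the efficacy analyses". The endpoints in that section are LDL-C, Apo B, non-HDL-C, TC and TG.

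SAP 4.9 lists HDL-C, Apo A1, the Apo B/Apo A1 ratio, Lp(a) and Apo CIII as other variables, for example "The percent change in Apo B/Apo A1 ratio from baseline over time" and "The percent change in Lp(a) from baseline over time". SAP 5.9 gives their data rule: "All measurements, scheduled or unscheduled, fasting or not fasting, will be assigned to Global Analysis Windows". It does not mention apheresis.

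SAP 6.4 chooses among several values in a window by distance from the target day, with ties going to the later value. If several values fall on one day, it takes the first when times are recorded. SAP 6.5 lets unscheduled values fill a time point, including baseline, where appropriate.

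On conduct, Protocol 5.1 and footnote 3 to Table 3 require samples to be drawn before apheresis. For time since the last procedure, Protocol 5.1 says that "it is important to match the time of the baseline activities with the timing of the week 24 activities". Protocol 8.2.3.2 says the specialty panel is run on the lipid-panel sample.

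**The concern.** Protocol 5.1 itself says that apheresis affects lipid parameters. The SAP backs the sampling rule with a data rule, but that rule is narrow in two ways.

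- **Time.** It stops at midnight. A sample taken the next morning is not excluded.
- **Variables.** It is stated only for the secondary endpoints. Apo B from a post-apheresis tube is removed, but a ratio with that same Apo B as numerator is not.

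With one arm, no control group would reveal or cancel an apheresis artefact. Only apheresis patients are affected, so the summary by apheresis status in SAP 5.7.2 is the most exposed. The adolescent summaries are also sensitive, because about 14 patients are planned and one value carries weight.

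**Working it through.** The plan gives no figure to reproduce: no sample size was calculated, and the point concerns the scope of a data rule.

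**1. Scope, side by side**

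| Measured in one sample | SAP section | Apheresis exclusion stated there | Declared not an efficacy variable in the Protocol |
|---|---|---|---|
| LDL-C, Apo B, non-HDL-C, TC, TG | 4.7.2 | Yes, same day only | No |
| HDL-C | 4.9, 5.9 | No | Yes (8.2.3) |
| Apo A1 | 4.9, 5.9 | No | Yes (8.2.3.2) |
| Apo B/Apo A1, Lp(a), Apo CIII | 4.9, 5.9 | No | No |

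If a pre-procedure sample exists on the same day and times are recorded, SAP 6.4 picks it, and the SAP 4.9 variables are protected too. The split within one tube arises when the post-procedure draw is the only one that day.

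**2. Selection rule**

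Take a pre-apheresis sample at target day + d, with d from -7 to +7 (the visit window), and a second sample the next day at d + 1. Both lie inside the 28-day analysis window in SAP Table 1. The later sample is chosen when |d + 1| < |d|, that is for d = -7 to -1. This is 7 of the 15 offsets, and the same-day exclusion removes none of them. If the next-day sample is the only one in the window, it is used whatever d is.

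**3. Where such a sample can arise**

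- Matching of time since apheresis is required for baseline and week 24 only. Table 3 also schedules lipids at weeks 8, 12 and 16, visits B, C, D and F, end of treatment, and 12 and 24 weeks after the last dose.
- Early-termination visits are timed to within 5 days of discontinuation, without reference to apheresis.
- The screening footnotes ask for a draw immediately before the procedure. Footnote 3 to Table 3 says only before, so a draw the day after one session is still before the next.
- For patients from R1500-CL-1629, the analysis baseline lies in the parent study (SAP 6.1). These documents do not show that the matching rule reaches it.

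**4. Direction and size**

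Let r and r0 be the residual apheresis reductions in the post-baseline and baseline samples. With the 47% LDL-C reduction reported for R1500-CL-1629 (Protocol Section 1):

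observed change = 100 × [(1 − 0.47)(1 − r)/(1 − r0) − 1]

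The documents give neither r nor r0, so the range of 10% to 60% is an assumption.

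- Post-baseline only (r0 = 0): r = 10% gives -52.3%, 20% gives -57.6%, 40% gives -68.2% and 60% gives -78.8%. The shifts are -5.3, -10.6, -21.2 and -31.8 points.
- Baseline only (r = 0): r0 = 20% gives 0.53/0.80 − 1 = -33.8%, and r0 = 40% gives 0.53/0.60 − 1 = -11.7%. Drug effect is hidden.
- Equal timing (r = r0): -47.0% whatever r is. There is no bias.

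One post-baseline-affected patient moves a mean of 14 by 5.3/14 = 0.4 to 31.8/14 = 2.3 points, and a mean of 120 by 0.04 to 0.27 points. For Lp(a), the ratio and Apo CIII the documents give neither the drug effect nor the apheresis effect, so no figure can be computed.

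**The case against.** The protocol largely prevents the problem. Pre-procedure sampling is mandatory, and footnote 3 is attached to both lipid panels at all treatment visits. Samples also precede dosing, and dosing is tied to the procedure: immediately after it, or one day before. A compliant dosing-visit sample is therefore normally drawn shortly before apheresis. The same footnote lets the visit window give way to apheresis timing. Unscheduled values are used only where appropriate, and deviations that may affect efficacy are reviewed (SAP 4.6). This stands as to frequency. A post-apheresis value needs a deviation, an unscheduled draw, or a visit not tied to dosing, such as early termination or follow-up.

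The exclusion can also be read more widely. It speaks of any lipid values and of efficacy analyses, and the protocol places the specialty panel under efficacy. On that reading Lp(a), Apo CIII and the ratio are covered. The all-measurements phrase is windowing language that SAP 4.7.2 also uses just after its own exclusion. This is a fair alternative for those three variables. It does not help HDL-C or Apo A1, which the protocol says are not efficacy variables, and an exclusion that needs this argument should be written out.

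A reader might infer that the main analysis should keep only values drawn at each patient's usual apheresis interval. The documents do not support that. Apheresis may be adjusted after week 24. The ±1 and ±2 day tolerances govern spacing of procedures, not sampling. No section shows that every session date is captured. SAP 4.7.2 also uses values regardless of subsequent therapies.

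**Conclusion.** The gap in scope is real and rests on the text alone: a same-day limit, and no stated exclusion for HDL-C, Apo A1, Apo B/Apo A1 and, on the plain reading, Lp(a) and Apo CIII. A value drawn a day or two after apheresis can enter a summary without breaking any SAP rule.

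A reader might infer that the results will show an apheresis effect as an evinacumab effect. The documents do not support that. Overstatement occurs only when the post-baseline sample is closer to apheresis than the baseline sample. The reverse understates the effect, and equal timing cancels it. The frequency is unknown and probably low, and the sizes above depend on the assumed 10% to 60% residual reduction.

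This is a cheap improvement of low-to-moderate severity. Efficacy is secondary and descriptive with no formal testing, and one affected value barely moves a mean of 120, though it can move the adolescent mean visibly.

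**What to change.** 1. In SAP 5.9, state that the post-apheresis exclusion of SAP 4.7.2 applies, at baseline and post-baseline, to every lipid and apolipoprotein from the sample, naming HDL-C, Apo A1, Apo B/Apo A1, Lp(a) and Apo CIII.
2. Where session dates are recorded, derive days since the last apheresis. List values in apheresis patients whose interval differs from that of their baseline sample. Fix the tolerance before database lock, since the documents give none for sampling. Repeat the LDL-C percent-change summary without these values, overall, in the apheresis subgroup and in adolescents, as a sensitivity analysis. Leave the main analysis otherwise unchanged.

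For R1500-CL-1629 patients the baseline interval needs the parent-study session date. Where it is missing, list the interval as unknown.

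The cost is a sentence in SAP 5.9, one derived variable, one listing and one extra summary, with the loss of a few values for the SAP 4.9 variables.

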4.8. Other Safety Variables

The other safety variables include clinical laboratory data, vital signs, and ECG. Unless otherwise noted, the baseline value is defined according to the definition of baseline specified in Section 6.1.

4.8.1. Adverse Events Variables

The period of safety observation starts from the time when the patient gives informed consent and continues into the following periods:

- The PRE-TREATMENT period is defined from the day the ICF is signed to the day before the first dose of open-label study treatment administration.
- The open-label treatment-emergent adverse event (TEAE) period is defined from the day of the first open-label study treatment administration to the day of the last open-label study treatment administration + 168 days (24 weeks).
- The POST-TREATMENT period is defined from the day after the end of the TEAE period to the last study visit.

4.8.1.1. Adverse Events and Serious Adverse Events

Adverse events (including serious adverse events (SAE), AEs causing permanent treatment discontinuation, deaths, and AEs of special interest) are recorded from the time of signed informed consent until the end of study. All AEs diagnosed by the Investigator will be reported and described.

All AEs will be dictionary coded by “lowest level term (LLT)”, “preferred term (PT)”, “high level term (HLT)”, “high level group term (HLGT)” and associated primary “system organ class (SOC)” using the version of MedDRA in effect at the time of the first database lock.

Adverse Event Observation Period

- Pre-treatment AEs are AEs that developed or worsened or became serious during the pre-treatment period.
- Open-label TEAEs are AEs that developed or worsened or became serious during the open-label TEAE period.
- Post-treatment AEs are AEs that developed or worsened or became serious during the post-treatment period.

4.8.1.2. Adverse Events of Special Interest

Adverse events of special interest (AESI) are AEs (serious or non-serious) required to be monitored, documented, and managed in a pre-specified manner. AESIs will be recorded on the adverse event e-CRF using dedicated tick boxes, and/or identified using standard MedDRA queries (SMQ), company MedDRA queries (CMQ), MedDRA terms, and/or applicable laboratory assessments. Appendix 10.3 contains the definitions used to identify AESIs:

The AESIs include:

- Anaphylactic reactions (e-CRF)
- General allergic events (SMQ)
- Infusion reactions (e-CRF)
- Hepatic Disorder (SMQ, lab data)
- Pregnancy (e-CRF)
- Symptomatic overdose with investigational medicinal product (e-CRF)
- Neurocognitive events (CMQ)
- Neurologic events (e-CRF)
- New onset of diabetes (NOD) (lab data, MedDRA HLT, concomitant medications) for patients without diabetes mellitus at baseline
- Diabetic complication (CMQ, concomitant medications) for patients with diabetes mellitus at baseline
- Pancreatitis (e-CRF)
- Cataracts (MedDRA HLT)
- Immune complex diseases (SMQ)
- Muscle events/CK elevation (MedDRA SOC, SMQ, lab data)

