9.3.4. Infusion Reactions

Infusion reactions are defined as any relevant AE that occurs during the infusion or within 2 hours after the infusion is completed. All infusion reactions must be reported as AEs (defined in Section 9.4.1) and graded using the grading scales as instructed in Section 9.5.1.

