9.4.3. Other Events that Require Accelerated Reporting to Sponsor

The following events also require reporting to the sponsor (or designee) within 24 hours of learning of the event:

Symptomatic Overdose of Study Drug: Accidental or intentional overdose of at least 2 times the intended dose of study drug within the intended therapeutic window, if associated with an AE,

Pregnancy: Although pregnancy is not considered an AE, it is the responsibility of the investigator to report to the sponsor (or designee), within 24 hours of identification, any pregnancy occurring in a female patient or female partner of a male patient, during the study or within 24 weeks of the last dose of study drug. Any complication of pregnancy affecting a female study patient or female partner of a male study patient, and/or fetus and/or newborn that meets the SAE criteria must be reported as an SAE. Outcome for all pregnancies should be reported to the sponsor.

Adverse Events of Special Interest: All AESI, serious and nonserious, must be reported within 24 hours of identification using the same reporting process as for SAE reporting, per Section 9.4.2.

Adverse events of special interest for evinacumab include the following:

- Anaphylactic reactions
- Moderate or severe infusion reactions

- Increase in ALT or AST: ≥ 3 x ULN (if baseline <ULN), or ≥ 2 times the baseline value (if baseline \geq ULN)
- Allergic events and/or local injection site reactions that require medical treatment or that require consultation with another physician for further evaluation
- Pregnancy
- Symptomatic overdose with investigational medicinal product
- Neurocognitive events
- New onset of diabetes*
- Pancreatitis

Adverse events of special interest for alirocumab include the following:

- Increase in ALT: ALT ≥ 3 x ULN (if baseline ALT <ULN), or ALT ≥ 2 times the baseline value (if baseline ALT \geq ULN)
- Allergic events and/or local injection site reactions that require consultation with another physician for further evaluation
- Pregnancy
- Symptomatic overdose with investigational medicinal product
- Neurologic events that require additional examinations/procedures and/or referral to a specialist
- Neurocognitive events
- Cataracts
- New onset of diabetes*

*New onset of diabetes is defined as any of the following:

- Type 1 or type 2 diabetes TEAE (grouping of MedDRA terms will be specified in the statistical analysis plan [SAP])

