9.5. Evaluation of Severity and Causality

9.5.1. Evaluation of Severity

The severity of AEs will be graded according to the following scale:

Mild: Does not interfere in a significant manner with the patient normal functioning level. It may be an annoyance. Prescription drugs are not ordinarily needed for relief of symptoms, but may be given because of personality of the patient.

Moderate: Produces some impairment of functioning but is not hazardous to health. It is uncomfortable or an embarrassment. Treatment for symptom may be needed.

Severe: Produces significant impairment of functioning or incapacitation and is a definite hazard to the subject's health. Treatment for symptom may be given and/or patient hospitalized.

If a laboratory value is considered an AE, its severity should be based on the degree of physiological impairment the value indicates.

Infusion Reactions

The severity of infusion reactions will be graded according to the following scale (semi-colon indicates “or” within description of the grade):

Mild: Mild transient reaction; infusion interruption not indicated; intervention not indicated.

Moderate: Therapy or infusion interruption indicated but responds promptly to symptomatic treatment (eg, antihistamines, NSAIDs, narcotics, IV fluids); prophylactic medications indicated for ≤ 24 hours.

Severe: Prolonged (eg, not rapidly responsive to symptomatic medication and/or brief interruption of infusion); recurrence of symptoms following initial improvement; hospitalization indicated for clinical sequelae; life-threatening consequences; urgent intervention indicated; death.

Injection Site Reactions

The severity of injection site reactions will be graded according to the following scale (semi colon indicates “or” within description of grade):

Mild: Pain that does not interfere with activity; mild discomfort to touch; < 5 cm of erythema or induration that does not interfere with activity.

Moderate: Pain that requires repeated use of non-narcotic pain reliever > 24 hours or interferes with activity; discomfort with movement; 5.1 cm to 10 cm erythema or induration or induration that interferes with activity.

Severe: Pain that requires any use of narcotic pain reliever or that prevents daily activity; significant discomfort at rest; > 10 cm erythema or induration; prevents daily activity; requires ER visit or hospitalization; necrosis or exfoliative dermatitis.

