5.8.2. Analysis of Adverse Events of Special Interest

- Treatment-emergent adverse events of special interest (AESI), as listed in Section 4.8.1.2, will be presented by SOC and PT as applicable. AESI are defined by SMQ, CMQ, and/or dedicated e-CRF as described in Appendix 10.3 .

The following variables will also be tabulated for infusion reactions TEAEs:

- Intensity of the event (mild, moderate, severe or very severe);
- Number of events divided by the number of study treatment administrations received in treatment period;
- Time from first study treatment to first infusion reaction;

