10.3. List of AESIs with Data Sources and Definitions of SMQ/CMQ

Table 2: Summary of AESIs and the Methods of Data Collections and Derivations

AESI	Using an e-CRF specific tick box on AE page	Using Standard MedDRA Query (SMQ)/company MedDRA Query (CMQ) or lab data
Anaphylactic reactions	Yes	No
General allergic events	No	SMQ “hypersensitivity” (broad and narrow) excluding the following preferred terms linked to local injection site reactions (“infusion site dermatitis”, “infusion site hypersensitivity”, “infusion site rash”, “infusion site urticaria”, “injection site dermatitis”, “injection site hypersensitivity”, “injection site rash”, “injection site urticaria”, “injection site vasculitis”) plus “idiopathic angioedema”
Infusion reactions	Yes	No
Hepatic Disorders	No	
 • SMQ Drug-related hepatic disorder • Potentially clinically significant value (PCSV) in Appendix 10.4 • Hy’s law eDISH plot
Pregnancy	Yes	No
Symptomatic overdose with investigational medicinal product	Yes	No
Neurocognitive events	Yes	
 • CMQ for neurocognitive events as defined based on Regulatory Agency request for another lipid lowering program (See Table 3 in Appendix 10.3 for the list of terms)
Neurologic events	Yes	No

AESI	Using an e-CRF specific tick box on AE page	Using Standard MedDRA Query (SMQ)/company MedDRA Query (CMQ) or lab data

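### The protocol limits the infusion reaction AESI to moderate or severe events, while the SAP sets no limit and finds them only by an AE-page tick box whose scope the documents do not define

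*SAP*

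**What the plan says.** **Protocol.** Section 9.3.4 defines the event by timing and relevance: "Infusion reactions are defined as any relevant AE that occurs during the infusion or within 2 hours after the infusion is completed". It adds that "All infusion reactions must be reported as AEs" and refers to Section 9.5.1 for grading. Section 9.5.1 gives infusion reactions their own three-grade scale, whose lowest grade is "Mild transient reaction; infusion interruption not indicated; intervention not indicated". Section 9.4.3, which sets 24-hour reporting to the sponsor, lists "Moderate or severe infusion reactions" among the AESIs for evinacumab. Section 10.4.4.1 cites Section 9.4.3 for the AESI summary. Section 3.2.3 includes infusion reactions in the identified risk of systemic hypersensitivity.

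**SAP.** Section 4.8.1.2 lists "Infusion reactions (e-CRF") as an AESI without a severity limit. It says that "AESIs will be recorded on the adverse event e-CRF using dedicated tick boxes", and/or identified through MedDRA queries, MedDRA terms or laboratory data. In Table 2 (Section 10.3), infusion reactions have Yes under "Using an e-CRF specific tick box on AE page" and No under the query and laboratory column. Section 5.8.2 then tabulates three items for them: "Intensity of the event (mild, moderate, severe or very severe"), events per infusion given, and time from first treatment to first reaction.

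**The concern.** The event that the SAP calls an AESI is not the event that the protocol calls an AESI, and the only route by which the SAP finds it is a box attached to the AESI concept. An investigator guided by Protocol 9.4.3 has no stated reason to tick that box for a mild reaction. An investigator guided by Protocol 9.3.4 would tick it for any reaction.

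At stake is how a named identified risk is described. Its severity profile, rate per infusion and time to first reaction could depend on how each site reads one e-CRF item. A sparse mild row could then reflect ascertainment rather than tolerability, and a reader could not tell which.

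**Working it through.** The documents state no infusion reaction rate and no severity split, so there is no figure to reproduce. The check is a comparison of the texts.

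| Source | Severity covered | How the event is found |
|---|---|---|
| Protocol 9.3.4 with 9.5.1 | Any; a mild grade exists | AE during the infusion or within 2 hours after it |
| Protocol 9.4.3 (cited by 10.4.4.1) | Moderate or severe | Expedited AESI report |
| SAP 4.8.1.2 | No limit stated | e-CRF |
| SAP Table 2 | No limit stated | Tick box only; no query or laboratory search |
| SAP 5.8.2 | Mild to very severe | Whatever the box returned |

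1. **Is mild in scope as an infusion reaction?** Section 9.3.4 does not mention severity. The mild grade in Section 9.5.1 shows that mild reactions are included.
2. **Is mild in scope as an AESI?** Not in Protocol 9.4.3. In the SAP it is, because the list has no limit and the table has a mild level.
3. **What if the box is ticked only for protocol AESIs?** Mild reactions do not enter the Section 5.8.2 outputs, and Table 2 provides no second search to recover them. Neurocognitive events, by contrast, have both a box and a query.
4. **What if the box is ticked for any grade?** The Section 5.8.2 outputs match Protocol 9.3.4, but the AESI total contains mild events that Protocol 9.4.3 excludes.
5. **What if sites differ?** The outputs mix the two sets.
6. **Why do the texts differ?** The SAP is signed 31 October 2019 and appends the schedules of Amendments 5A and 5B. The amendment log, used only as background, places the moderate-to-severe AESI entry in Amendment 6. That explains the mismatch but does not resolve it in the current texts.

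**Illustration only; the inputs below are assumed.** Let *m* be the mild share, with every mild event left unticked. The recorded rate is then the any-grade rate × (1 − *m*). Take 120 patients × 7 infusions (day 1 to week 24) = 840 infusions and an assumed 1 reaction per 100 infusions, so 840 × 0.01 = 8.4 expected events. The table would hold:

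- *m* = 25%: 8.4 × 0.75 = 6.3
- *m* = 50%: 8.4 × 0.50 = 4.2
- *m* = 75%: 8.4 × 0.25 = 2.1

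This follows directly from the assumption and is not evidence of any actual loss.

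**The case against.** The strongest reply is that the box may already mean any infusion reaction. The SAP names the item without limit and plans a mild row, and the protocol requires every infusion reaction to be reported and graded. On that reading nothing is missing from the table. Protocol 9.4.3 is also an expedited-reporting rule, and an analysis category wider than a reporting trigger is not in itself an error. The intensity rows let a reader pick out the moderate or severe events.

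Much of this stands. The e-CRF and its completion guide were not among the documents, so the narrow reading cannot be asserted. But the wide reading is not stated either, and under it the SAP's AESI still differs from the set that Protocol 10.4.4.1 points to. The rate per infusion and the time to first reaction are not split by severity in either case.

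Three stronger readings are tempting, and the documents support none of them:

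- **Mild reactions are lost from the study.** They must be reported as AEs and stay in the all-TEAE tables. Some would also fall under the hypersensitivity query, although Table 2 removes several infusion-site terms from it.
- **The two definitions cannot give the same count.** They agree if no mild reaction occurs, and the intensity rows allow the subset to be recovered if the box covers any grade.
- **The rate is understated by a known amount.** No mild share is given. It may be modest, since Protocol 7.4.1.1 calls for interruption for many listed signs, and Section 9.5.1 makes an indicated interruption a mark of the moderate grade.

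**Conclusion.** The concern holds as a conflict between current texts on an identified risk. The protocol's AESI is moderate or severe, the SAP's is unrestricted, and the SAP's sole means of finding the events is a box of undefined scope. One of two consequences follows if any mild reaction occurs: mild events are absent from the dedicated table, rate and time to first reaction, or the SAP's AESI count is wider than the protocol's. Which one applies depends on the e-CRF instructions.

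The size cannot be derived from the documents. The effect is confined to the dedicated infusion reaction outputs and the AESI count; overall TEAE reporting is unaffected. The most likely cause is a SAP not yet brought up to Amendment 6. Protocol Section 10 and SAP Section 1 both provide for revising the plan before database lock, so it should be aligned then.

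**What to change.** In SAP 4.8.1.2, Table 2 and 5.8.2:

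- Define the infusion reaction set as every AE meeting Protocol 9.3.4, at any grade.
- State that the tick box applies to all of these, whether or not they meet the Protocol 9.4.3 reporting trigger.
- Define the AESI as the moderate or severe subset, derived from the recorded grade.
- Base the intensity table, the rate per infusion and the time to first reaction on the any-grade set, and report the AESI subset rate beside it.
- Align the intensity levels with the three grades in Protocol 9.5.1 by dropping the very severe level, which that scale does not contain.

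An optional data check is a listing of unticked AEs with onset during the infusion or within 2 hours after it, where times are recorded. A full programmed search with medical review is not needed to resolve the conflict.

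The cost is minor SAP wording and programming. If the listing is run, some onset times may be missing.
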